## SYNOPSIS

**Title of trial:** A Phase I/II Dose-escalation and Expansion Cohort Trial of Intracerebroventricular Radioimmunotherapy Using Lu-DTPA-omburtamab in Pediatric and Adolescent Patients with Recurrent or Refractory Medulloblastoma

**Indication:** Recurrent or refractory medulloblastoma.

**Number of investigators and trial centers:**

Part 1 will be conducted at approximately 9 sites: 4 sites in North America and 5 in Europe

Part 2 is planned to be conducted at approximately 2 additional sites in North America and Europe

**Development phase:** Phase I/II

**Objectives:**

The primary objective of Part 1 (dose-escalation phase) is to explore the tolerability of up to 2 cycles of intracerebroventricular Lu-DTPA-omburtamab treatment in pediatric and adolescent patients with recurrent or refractory medulloblastoma. The maximum tolerated dose (MTD) and/or the recommended Phase 2 dose for Part 2 (RP2D) will be determined.

The primary objective of Part 2 (cohort-expansion phase) is to establish a safety profile of repeated dosing of Lu-DTPA-omburtamab in pediatric and adolescent patients with recurrent or refractory medulloblastoma.

The secondary objectives of Part 1 are:

- to evaluate the absorbed radiation doses to cerebrospinal fluid (CSF) and blood of Lu-DTPA-omburtamab after intracerebroventricular administration
- to evaluate organ dosimetry of Lu-DTPA-omburtamab
- to evaluate the pharmacokinetic (PK) profile of Lu-DTPA-omburtamab.

The secondary objectives of Part 2 are:

- to evaluate the PK profile of Lu-DTPA-omburtamab
- to evaluate the investigator-assessed response
- to evaluate the investigator-assessed DoR
- to evaluate PFS
- to evaluate overall survival (OS).

**Methodology/trial design:**

This is a Phase I/II, open-label, safety and efficacy trial in pediatric and adolescent patients (3 to 19 years) with recurrent or refractory medulloblastoma.

Part 1 will be a dose-escalation phase with a 3+3 sequential-group design (except for the first dose level, which will consist of a single patient only), in which patients will receive a maximum of two 5-week cycles of treatment with intracerebroventricular Lu-DTPA-omburtamab. A Data Monitoring Committee will review the safety data from previous dose levels and provide recommendations on whether dose escalation should continue. In Part 1, Cycle 1 will comprise a dosimetry dose on Day 1 and a treatment dose on Day 8, while Cycle 2 will comprise a treatment dose on Day 1. Successive dosing groups will receive escalating treatment doses of lutetium-177 conjugated to a fixed mass dose of approximately 1 mg DTPA-omburtamab; the dosimetry dose will be fixed for all patients.

Part 2 will be a cohort-expansion phase in which patients will receive a maximum of 5 cycles of intracerebroventricular Lu-DTPA-omburtamab at the RP2D determined in Part 1. All cycles in Part 2 will comprise a treatment dose on Day 1.

The AEs will be evaluated according to CTCAE version 5.0.

### Number of patients:

In Part 1, the chosen sample size is customary for dose-escalation studies of this nature and is not based on statistical considerations. It is estimated that up to 25 patients will participate in Part 1. Actual number of patients will depend on the number of dose-limiting toxicities (DLTs) observed. In Part 2, 24 patients are expected to participate, which will provide at least 90% probability to detect an adverse event (AE) occurring in 10% of exposed patients. The assumption is that 20 out of the 24 patients in Part 2 are evaluable. With 20 patients evaluable for response and a response rate of 25% (~ to 5 responders out of 20), the lower limit of the 95% confidence interval will be 9%.

### Key criteria for inclusion and exclusion:

The key inclusion criteria are:

1. Histologically confirmed diagnosis of medulloblastoma.
2. SHH, Group 3, or Group 4 according to World Health Organization 2016 classification.
3. Recurrent or refractory to frontline therapy, defined as:
  - a. For Part 1 only: Recurrent (maximum of 2 recurrences) or refractory to frontline therapy. Prior frontline or second-line therapy may involve surgery, craniospinal irradiation, stereotactic radiosurgery, and multi-agent chemotherapy regimens.
  - b. For Part 2 only: Recurrent (maximum of 1 recurrence) or refractory to frontline therapy. Patients with recurrent disease must have received second-line chemotherapy for progressive disease. Prior frontline or second-line therapy may involve surgery, craniospinal irradiation, stereotactic radiosurgery, and multi-agent chemotherapy regimens.
4. Have refractory disease, focal or multifocal recurrent disease, or pure leptomeningeal disease. Cytological or radiographic remission is allowed; however, not simultaneously.
5. Performance status score of 50 to 100, both inclusive, on the Lansky [<16 years] or Karnofsky [≥16 years] scales.
6. Aged 3 to 19 years, both inclusive, at the time of the first planned dose of trial treatment.
7. Life expectancy of at least 3 months, as judged by the investigator.
8. Acceptable liver and kidney function and hematological status.
9. Written informed consent from legal guardian(s) and/or child obtained in accordance with local regulations. Pediatric patients must provide assent as required by local regulations.

The key exclusion criteria are:

1. Obstructive or symptomatic communicating hydrocephalus as determined by Ommaya patency/CSF flow assessment.
2. Any tumor lesion measuring >15 mm in the smallest diameter.
3. Ventriculoperitoneal shunts without programmable valves. Ventriculo-atrial or ventriculo-pleural shunts.
4. Grade 4 nervous system disorder. Stable neurological deficits due to brain tumor or surgery and hearing loss are allowed.
5. Uncontrolled life-threatening infection.
6. Received radiation therapy (focal or cranio-spinal irradiation), systemic or intrathecal cytotoxic chemotherapy, or immunotherapy (including monoclonal antibodies; corticosteroids not included) less than 3 weeks prior to the Dosimetry Dose (or until recovery from clinically significant adverse events). Received nitrosoureas less than 6 weeks prior to the Dosimetry Dose.
7. Received any prior anti-B7-H3 treatment.
8. Non-hematologic organ toxicity Grade 3 or above; specifically, any renal, cardiac, hepatic, pulmonary, and gastrointestinal system toxicity.

9. Other significant disease or condition that in the investigator's opinion would exclude the patient from the trial.
10. Females of childbearing potential, who are pregnant, breast feeding, intend to become pregnant, or are not using highly effective contraceptive methods or males who are not using highly effective contraceptive methods.

**Test products, dose, and mode of administration:**

Local safety instructions for storage and handling of radioactive drug products must be strictly followed. Radiation safety precautions may include patient isolation and the use of lead shielding, or designated rooms to ensure that the dose rate in the surrounding areas meets regulatory requirements.

Lu-DTPA-omburtamab will be administered via an indwelling intracerebroventricular access device (e.g., Ommaya catheter). The infusion reservoir must be flushed with human serum albumin (HSA) and CSF after each infusion. To avoid an additional procedure and burden to the patient, it can be considered to place the intracerebroventricular access device in connection with any tumor resection procedure that may be performed before entry into the trial. In this case, the informed consent form must be signed before the tumor resection.

In Part 1 only, at the start of the first 5-week treatment cycle, a 5 mCi dosimetry dose will be administered on Day 1. If the dosimetry dose of 5 mCi delivers a too low acquisition of radioactivity count, the dosimetry dose will be increased to 10 mCi for subsequent patients, at the Sponsor's discretion. A treatment dose with a fixed mass dose of approximately 1 mg DTPA-omburtamab will be labelled with increasing radioactivity doses of lutetium-177 and will be administered on Day 8 of Cycle 1. The planned radioactivity dose levels in the escalation phase are:

- Dose Level 1 (1+2 patients): 10 mCi
- Dose Level 2 (3+3 design): 25 mCi
- Dose Level 3 (3+3 design): 50 mCi
- Dose Level 4 (3+3 design): 65 mCi
- Dose Level 5 (3+3 design): 85 mCi

A maximum of 1 additional intermediate dose level may be added to the trial if warranted based on the findings from previous dose levels. If a patient experiences a Grade 3 or 4 non-hematologic AE or other DLTs after receiving the dosimetry dose, the treatment dose will not be administered, and the patient will be discontinued from trial treatment. Patients who are not discontinued from treatment will be eligible for 1 additional treatment cycle with the same dose as administered in the first cycle. The second treatment cycle of Part 1 will consist of a treatment dose on Day 1.

In Part 2, all treatment cycles will consist of a treatment dose on Day 1; the dose level will be the RP2D determined in Part 1. Patients who are not discontinued from treatment will be eligible for up to 5 treatment cycles in Part 2. Dose reductions due to toxicity are permitted in Part 2 only.

**Reference therapy, dose, dose form, and mode of administration:**

Not applicable.

**Duration of patient participation in trial:**

Planned screening duration: 29 days (longer screening period is allowed (e.g., due to logistics); however, screening period of >60 days with individual patient considerations to be discussed with the sponsor.

Planned treatment duration: Up to two 5-week treatment cycles may be administered in Part 1 and up to five 5-week cycles may be administered in Part 2.

Planned duration of trial participation: 19 weeks (Part 1); 104 weeks (Part 2).

Estimated recruitment period: Q4-2021 to Q3-2023.

**Analysis populations:**

The following analysis sets will be included for this trial:

**Safety Analysis Set:** will consist of all patients who received at least 1 dosimetry or treatment dose.

**DLT Evaluable Analysis Set:** will include patients in the dose escalation who as a minimum is evaluated during the 5 weeks DLT evaluation period, or who has a DLT during the DLT evaluation period. This analysis set is a subset of the Safety Analysis Set.

**Full Analysis Set (FAS):** will consist of all patients in the Safety Analysis Set.

**Dosimetry Analysis Set (Part 1 only):** will consist of all patients who received the dosimetry dose and have evaluable data for absorbed doses to CSF and blood or by whole-body planar scan.

**PK Analysis Set:** will consist of all patients who received at least 1 treatment dose of trial drug and have evaluable pharmacokinetic (PK) data.

### **Evaluation: Safety**

Primary Endpoint:

- Part 1: Number of DLTs.
- Part 2: Number and severity of TEAEs.

### **Evaluation: Efficacy**

The secondary efficacy endpoints are:

Part 2

- Response, as defined by the RAPNO criteria (as determined from MRI assessments, neurological examination, and CSF cytology).
  - ORR calculated as the proportion of all evaluable patients achieving a response (PR or CR) as best overall response at the time of assessment.
- Investigator-assessed DoR, defined as the time from response (CR or PR) to progression.
- PFS defined as the time from first treatment to date of leptomeningeal progression or death from any cause, whichever comes first.
- OS defined as the time from first treatment to date of death.

### **Evaluation: Vital signs and other safety procedures**

Patients will undergo monitoring for AEs; vital sign assessments; neurological assessments and radiographical investigation for evaluation of neurological AEs); and assessment of performance status (Lansky [ $<16$  years] or Karnofsky [ $\geq 16$  years] scales).

### **Evaluation: Dosimetry, imaging, and laboratory evaluations**

Patients will undergo:

- Clinical chemistry and hematology assessments.
- Blood and CSF draws for calculation of absorbed doses (Part 1 only).
- Whole-organ dosimetry measurements based on gamma (and SPECT, if possible) scans (Part 1 only).
- Brain and spine MRI.
- CSF sampling for cytology, total protein, glucose, circulating tumor DNA (ctDNA; if the patient has given informed consent to this analysis), and cell count.
- Blood and CSF draws for PK; and blood and CSF draws for anti-drug antibody (ADA) analysis and for potential culture (in case of elevated body temperature).

### **Statistical methods:**

Summary statistics, listings, and statistical analyses will be performed for patients included in the relevant analysis sets. PFS will be censored at last disease evaluation with no evidence of progression. OS will be censored at last date known to be alive.

### **Efficacy statistical methods:**

The investigator-assessed response will be assessed in Part 2 according to RAPNO criteria (MRI, neurological examination, and CSF cytology), as well as according to CSF cytology alone. The ORR and its 95% confidence intervals will be calculated using the Clopper-Pearson exact methodology.

The investigator-assessed DoR will be estimated using Kaplan-Meier methods. The median DoR and corresponding 95% confidence interval will be calculated.

PFS time will be estimated using Kaplan-Meier methods. The median PFS time as well as the proportion of patients without PFS events at 1 and 2 years post first dose will be estimated in Part 2, along with their respective 95% confidence intervals.

Estimates of OS at 1 year and 2 years post first dose will be made in Part 2 only using Kaplan-Meier methods.

### **Safety statistical methods:**

Adverse events will be coded using the Medical Dictionary for Regulatory Activities (MedDRA) Version 22.1 or later. All AEs will be listed. Non-treatment-emergent AEs (Non-TEAEs) will be listed separately. All TEAEs, adverse drug reactions (ADRs), AEs of special interest, serious AEs, and serious ADRs will be summarized by system organ class and preferred terms for each treatment group. In Part 1, the DLTs will be listed.

Changes in vital signs, hematology, and clinical chemistry parameters from baseline to the end of the trial will be examined. Treatment-emergent changes from normal values to abnormal values in key laboratory parameters may be identified. Development of ADA will be examined. Effects on cognitive functions will be assessed by summarizing changes from baseline in performance testing results using descriptive statistics.

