## 6.3. Treatment of Expected Toxicities

### Premedication

Starting 24 hours prior to each Lu-DTPA-omburtamab infusion, dexamethasone will be administered orally at 0.6 mg/kg/day or an IV equivalent (subject to a maximum total dose of 20 mg/day) divided into twice-daily doses for a total of 3 days to alleviate infusion-related AEs.

An anti-pyretic (e.g., oral acetaminophen/paracetamol [15 mg/kg, 650 mg maximum]) and an antihistamine (e.g., diphenhydramine [1 mg/kg, 50 mg maximum]) or equivalents will be administered within 1 to 2 hours before all intracerebroventricular infusions.

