### **8.5.3. Other Safety Assessments**

Changes in vital signs, hematology, and clinical chemistry parameters from baseline to the end of the trial will be examined. Treatment-emergent changes from normal values to abnormal values in key laboratory parameters may be identified. Development of ADA will be examined. Effects on cognitive functions will be assessed by summarizing changes from baseline in performance testing results using descriptive statistics.

Baseline is defined as the latest assessment prior to first dose.

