## Appendix 3: Schedule of Assessments

**Table 6: Schedule of Assessments – Part 1, Screening and Cycle 1**

Dosing/Measurements/Evaluations	Screening	 Lu-DTPA-omburtamab Treatment Period  – Cycle 1				
	Day -29* to -1	Day 1	Day 8 (±1)	Day 15 (±1)	Day 22 (±1)	End-of-Cycle Visit (Day 29 [±1])
Informed consent 	X					
Eligibility check	X					
Demographics, height, body weight	X					
Medical, surgical, and disease history	X					
Prior/concomitant medications	X	X	X	X	X	X
Physical examination 	X					
Vital signs 	X	X	X	X	X	X
Performance test 	X 					
MRI of the brain and spine 	X 					
Neurological examination 	X	X				
Placement of indwelling ICV access device	X 					
ICV access device patency/CSF flow assessment	X					
Premedication (oral dexamethasone/IV equivalent) 		X	X			
Anti-pyretic and anti-histaminergic premedication 		X	X			
ICV  Lu-DTPA-omburtamab dosimetry dose		X				
ICV  Lu-DTPA-omburtamab treatment dose			X			
Whole-body planar gamma camera scan 		X 	X 	X 		
Blood and CSF for calculation of absorbed doses 		X 		X 		
Clinical chemistry and hematology 	X	X	X	X	X	X
CSF for cytology  , total protein, glucose, and cell count	X 					
Blood and CSF for culture		X 	X 			
Blood and CSF sampling for ADA 	X 					
Blood and CSF sampling for pharmacokinetics			X 	X 		
Pregnancy testing 	X	X	X			
Adverse events 	X	X		X	X	X

Abbreviations: ADA = anti-drug antibody; AE = adverse event; CSF = cerebrospinal fluid; ctDNA = circulating tumor deoxyribonucleic acid; EOT = end of treatment; HSA = human serum albumin; ICF = informed consent form; ICV = intracerebroventricular; IMP = investigational medicinal product; IV = intravenous; MRI = magnetic resonance imaging; NCI = National Cancer Institute; SAE = serious adverse event.

\* A longer screening period (e.g., due to logistics, COVID-19 situations etc.) are allowed; however, eligibility evaluation must be re-confirmed. Screening period of >60 days with individual patient considerations to be discussed with the sponsor.

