 The Lu-DTPA-omburtamab Treatment Period is divided into 5-week cycles. In Part 1, the patient can receive up to 2 cycles at the discretion of the investigator. Cycle 1 starts with a dosimetry dose on Day 1 and continues with the first treatment dose on Day 8 (adjustments to the dosing schedule will be accommodated on a patient-by-patient basis depending on the clinical condition of the patient). The infusion reservoir must be flushed with HSA and CSF after each infusion. On dosing days, all assessments are done before dosing.

 If the IMP is discontinued after Cycle 1, the Day 29 Visit is replaced by the EOT Visit.

 Informed consent must be obtained before any trial-related procedures. If the indwelling ICV access device (e.g., Ommaya) is placed in connection with the tumor resection, the informed consent must be obtained prior to the surgery, and before the start of the screening period, unless this is placed as part of a standard of care procedure at site. If any procedures/tests are from before informed consent is obtained, it must be clear from source documents that this was not performed for the purpose of the present trial. In these cases, the procedures/tests do not need to be repeated at the Screening Visit if they were performed within the allowed timelines. The investigator is responsible for documenting this properly.

 Physical examinations to be performed at screening and as clinically indicated.

 Measurements of heart rate, respiratory rate, temperature, and blood pressure. On dosing days, measurements to be taken before and 30 min after the end of the IMP infusion.

 Lansky Scale <16 years, Karnofsky Scale ≥16 years.

 To be performed within 3 weeks prior to the first IMP infusion. May be performed on the first dosing day but it must be before IMP administration.

 MRI of the brain and spine will be completed before first IMP administration, at the EOT Visit (preferably ±4 days of the actual visit date). MRI can be performed on a separate day to the other visit assessments, if required, in accordance with investigational site standards.

 Will be used to evaluate safety and efficacy.

 Beginning 24 hours before IMP administration, divided into twice-daily doses for a total of 3 days.

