 Measurements of heart rate, respiratory rate, temperature, and blood pressure. On dosing days, measurements to be taken before and 30 min after the end of the IMP infusion.

 Lansky Scale <16 years, Karnofsky Scale ≥16 years.

 To be performed within 3 weeks prior to first IMP infusion. May be performed on the first dosing day but it must be before IMP administration.

 MRI of the brain and spine will be completed before first IMP administration and at the End-of-Cycle (Day 29) Visit for Cycles 1 and 3 only (±4 days of the actual visit date), EOT Visit (preferably ±4 days of the actual visit date), and each Follow-up Visit (±2 weeks of the actual visit date). MRI can be performed on a different day to the other visit assessments, in accordance with investigational site standards.

 Will be used to evaluate safety and efficacy.

 Beginning 24 hours before Lu-DTPA-omburtamab administration, divided into twice-daily doses for a total of 3 days.

 Given 1-2 hours prior to Lu-DTPA-omburtamab administration, including oral acetaminophen/paracetamol and antihistamine (e.g., diphenhydramine).

 In accordance with [Appendix 1](#) and until the first follow-up visit.

 If CSF cytology sample is positive, it must be repeated within 4 weeks of the positive sampling.

 Cycles 1 and 3 only.

 Drawn and held for culture only if elevated body temperature after dosing suggests infection rather than expected response to ICV dosing. Samples to be taken within 6 hours after completion of Lu-DTPA-omburtamab infusion.

 The ADA samples must be drawn prior to dosing. Serum and CSF samples for ADA analyses will be drawn at baseline, at the start of Cycle 2 (predose), and after last treatment. Presence of ADA will be analyzed at a central laboratory.

 Blood and CSF samples for pharmacokinetics will be drawn in Cycles 1 and 2 only, as per [Table 5](#).

 Pregnancy testing (serum or urine) is mandatory for women of childbearing potential at screening, prior to each dose, and at the EOT Visit.

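### The Part 1 laboratory baseline is drawn during dexamethasone premedication, so white-cell and glucose changes to visits off premedication compare two different states

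*Combined protocol and SAP*

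**What the plan says.** The Synopsis (Safety statistical methods) and Section 8.5.3 plan the same analysis: "Changes in vital signs, hematology, and clinical chemistry parameters from baseline to the end of the trial will be examined". Both add that shifts from normal to abnormal in key laboratory parameters may be identified. Only Section 8.5.3 defines the starting point: "Baseline is defined as the latest assessment prior to first dose". The protocol defines no separate laboratory baseline.

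Tables 6 and 8 schedule chemistry and hematology at screening and again on Day 1. For Part 1, Table 6 footnote 1 fixes the order: "On dosing days, all assessments are done before dosing". The footnotes to Table 8 (Part 2) contain no such rule for laboratory draws.

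Under Section 6.3, "dexamethasone will be administered orally at 0.6 mg/kg/day or an IV equivalent", capped at 20 mg/day, starting 24 hours before every infusion and "divided into twice-daily doses for a total of 3 days to alleviate infusion-related AEs". Table 6 footnote 10 repeats the timing: "Beginning 24 hours before IMP administration, divided into twice-daily doses for a total of 3 days". Table 8 footnote 12 does the same for Part 2.

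For the baseline MRI, Table 6 footnote 7 and Table 8 footnote 9 set a 3-week window and add: "May be performed on the first dosing day but it must be before IMP administration".

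**The concern.** A change from baseline can be read as a treatment effect only if baseline and later value were taken under comparable conditions. Here the baseline rule picks a sample taken after premedication has begun, while several of the later samples are taken well after it has ended. The mismatch comes from the schedule, so it runs in the same direction in every patient and does not average out.

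The analytes most exposed matter in this trial. Section 1.2.1 reports at least one cytopenia-related event in 81.7% and 87.5% of patients in the two earlier trials of the iodine-labelled antibody, with lymphopenia and decreased white cells among the most common. If dexamethasone raises neutrophils, later falls look larger than they were. A child with a low count at screening could also appear normal on Day 1 and then be counted as a new shift. If it lowers lymphocytes, later falls look smaller, and a child already below normal on Day 1 cannot register as a normal-to-abnormal shift. A raised baseline glucose would hide a later rise. The plan has no alternative summary and does not discuss steroid effects on laboratory values.

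**Working it through.** The plan states no figure on this point, so the check is a timeline built from its own schedule.

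**Inputs.** Premedication starts 24 h before each infusion and lasts 3 days (Section 6.3), read here as -24 h to +48 h around the infusion. Part 1 infusions are on Day 1 (dosimetry dose) and Day 8 of Cycle 1, and on Day 1 of Cycle 2, which starts 35 days after the dosimetry dose (Table 7 footnote 1). Draw days come from Tables 6 to 8. Nominal time of a Cycle 1 draw = (day - 1) × 24 h.

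| Part 1 laboratory draw | Hours from first infusion | Premedication course (h) | State |
|---|---|---|---|
| Cycle 1 Day 1, pre-dose (baseline) | 0 | -24 to 48 | on |
| Cycle 1 Day 8, pre-dose | 168 | 144 to 216 | on |
| Cycle 1 Day 15 | 336 | none | off |
| Cycle 1 Day 22 | 504 | none | off |
| Cycle 1 Day 29 | 672 | none | off |
| Cycle 2 Day 1 | 35 × 24 = 840 | 816 to 888 | on |
| Cycle 2 Day 8 | 840 + 168 = 1008 | none | off |
| Cycle 2 Day 15 | 840 + 336 = 1176 | none | off |

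The EOT Visit is 5 to 6 weeks after the last dose: 35 × 24 = 840 h to 42 × 24 = 1008 h after it, so off.

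**Visit windows.** Take the least favourable ±1-day case in Cycle 1: second infusion on Day 9 (192 h), course ending at 192 + 48 = 240 h, and the Day 15 draw taken on Day 14 (312 h). The gap is still 312 - 240 = 72 h, so the classification stands.

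**Part 2.** Days 15 and 29 of a cycle fall 336 h and 672 h after that cycle's infusion: off. Day 1 of Cycles 2 to 5 is on. The Cycle 1 Day 1 draw is on premedication and becomes baseline only if taken before the infusion, which Table 8 does not state. If it were taken afterwards, the screening value would be baseline.

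**Effect on a reported change.** Let the baseline on premedication equal the true value B plus a shift d. For a later value Y off premedication, the reported change is Y - (B + d) = (Y - B) - d. The error is -d, one for one. At a visit on premedication with a similar shift, d largely cancels.

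**Size.** The documents give no value for d, so what follows is assumed and only shows the arithmetic (counts in 10⁹/L).

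- Neutrophils, assumed shift +1 to +4, true value 2.0, later value 1.0. The true change is -1.0. The reported change runs from 1.0 - 3.0 = -2.0 to 1.0 - 6.0 = -5.0.
- Lymphocytes, assumed fall of 30% to 60%, true value 1.0, later value 0.5. The baseline becomes 0.7 to 0.4. The true change is -0.5. The reported change runs from 0.5 - 0.7 = -0.2 to 0.5 - 0.4 = +0.1.

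**The case against.** Using the latest pre-dose value is a legitimate convention, and the screening value is not a clean substitute. Screening opens at Day -29 and may run longer, while the washout for chemotherapy and radiotherapy is 3 weeks (6 for nitrosoureas; exclusion criterion 6). A draw between Day -29 and Day -22 can therefore precede the last permitted cytotoxic dose or fall in recovery from it. Hematological support is allowed up to 1 week before dosing (inclusion criterion 8), so a screening platelet count or hemoglobin may predate a transfusion. Moving to screening also makes Day 8 of Cycle 1 and Day 1 of later cycles the mismatched visits. All of this stands. It argues against a wholesale change of baseline and for showing two baselines for a few analytes.

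The outputs are also descriptive, screening values remain in the data, and nothing tests or decides on these changes. That limits the weight of the point without removing it.

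A reader might infer more than the text supports:

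- That every change is mismatched. Draws on later dosing days share the baseline's state.
- That the baseline always follows a full day of steroid. No clock time is given for the draw, so 24 hours is an upper bound.
- That later samples are steroid-free. Corticosteroids are exempt from the washout and absent from the prohibited list in Section 6.2, so the contrast is on against off premedication only.
- That the neurological examination has the same flaw. Footnotes 7 and 9 attach to the performance test, MRI and CSF rows, and Section 8.5.3 plans no change summary for that examination.
- That response is thereby biased. Appendix 6 has its own steroid criterion for each response category. The narrower point is that an MRI on the first dosing day would be taken during premedication.

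**Conclusion.** The point holds as a limited one. In Part 1 the baseline rule selects a sample inside the premedication course, while Cycle 1 Days 15, 22 and 29, Cycle 2 Days 8 and 15 and the EOT Visit lie outside it. In Part 2 the same follows only if the first Day 1 draw precedes the infusion.

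The timing rests on the documents. The direction of the effect, and its confinement mainly to neutrophils, lymphocytes, total white cells and glucose, rest on general pharmacology. The size is unknown.

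The consequence is confined to the descriptive change and normal-to-abnormal summaries. A reader might infer that safety conclusions or dose decisions are compromised. The documents do not support that: the hematological DLT criteria in Section 3.1.1.2 are written as CTCAE grades, adverse events are summarised by severity, and escalation uses DLT counts. This is a low-cost improvement to planned safety tables, not a flaw in the design.

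**What to change.** 1. In Section 8.5.3, for white-cell count, differential and glucose, summarise change and shift from the last value before the first premedication dose (the screening sample already scheduled), and show the same summary from the Day 1 value. Visits off premedication are best read against the former and later dosing-day draws against the latter.
2. Keep the latest pre-dose value as baseline for platelets, hemoglobin and all other parameters.
3. State in Table 8 that the Day 1 laboratory draw is taken before the infusion.
4. In Table 6 footnote 7 and Table 8 footnote 9, have the baseline MRI used for response done before the first premedication dose.

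The laboratory changes cost wording and one extra summary for a few analytes: no new sample and no change to premedication. The screening value can be older and may reflect recovery from prior therapy, which is why both baselines are shown. The MRI window becomes about one day shorter.
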